6.2.4 Data collection

Participants will be given the option of completing a paper-based DCE survey or an online version. The online version will be hosted by the University of Oxford and monitored by the trial team in Oxford. The web version will comply with the required information governance standards of the University of Manchester.

6.2.5 Data Analysis

A sample of 2000 non-responding women will be included in the DCE survey. A sample size of 2000 will provide a precision of 0.25-0.75 in the standard errors of the model coefficients, and will allow the evaluation of setting sub-group (e.g. the impact of HPV vaccination on preferences). Several categorical dependent models will be evaluated, including multinomial logit / probit and conditional logit models, to obtain women's valuations and preferences.

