3.3 Planned Interventions

3.3.1 Pre-call cervical screening information leaflet (pre-leaflet)

Women in England aged 24 and a half years will be sent a bespoke information leaflet around six weeks prior to their first invitation. The content of this leaflet has been informed by focus groups and consultation exercises with women aged around 24 in Manchester and 19 in Aberdeen. The rationale will be to convert them from ‘pre-contemplators’ to ‘contemplators’ (based on the Transtheoretical model) by the time the standard NHSCSP invitation is received. This will deal with key themes and issues that emerged from the focus group and consultation work which has already been completed. Leaflets produced for use with the Aberdeen cohort will be sent to young women aged 19 years who are deciding whether to accept their invitation for cervical screening. They will have recently been offered HPV vaccination and the leaflet should be equally applicable to vaccinated women in England when they begin to receive their invitations 5 years from now.

In Manchester and Aberdeen the pre-leaflet will be sent to eligible women (i.e. those aged 24 and a half or 19 and a half) in randomised practices. This will be facilitated by the local screening agencies who maintain the population based register for the cervical screening programme and routinely have access to women’s details.

The outcome of this intervention will be the proportions of women screened in the intervention and control practices measured primarily at 2-3 months, prior to the first reminder and secondarily at 12 month. These data will be provided by the local screening agencies who routinely monitor the screening uptake in the practices within the boundaries of the Primary Care Trusts for which they are responsible. The screening agency will create an anonymised record for each woman involved in the trial using a unique identifier.

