- 3) Cost-effectiveness will be calculated. This will take two forms: One, the incremental cost per percentage point increase in screening attendance within the study time-horizon will be estimated for each of the strategies being examined compared to standard practice. Second, lifetime cost-effectiveness and cost-utility will be estimated. Construction of a new lifetime model is not proposed, as several validated models already exist and have been used to produce published estimates of the cost-effectiveness of the current screening programme. Instead, we propose to combine the cost and attendance results of the study with these published estimates of the lifetime costs and effects of participating in cervical cancer screening programmes, to obtain lifetime cost-effectiveness and cost-utility estimates. Results will be presented within a probabilistic framework, using cost-effectiveness acceptability curves and net-benefit statistics.

This approach will provide reliable estimates of cost and cost-effectiveness while adhering to the general approach of the project, which maximises use of routine data sources and minimises the need for direct contact with women participating in the study. The health economist would also be involved in the design and analysis of a discrete choice experiment (DCE). In 2013/2014, a sample of approximately 2000 non-responders to screening will be identified by the screening agency. These women will be invited to state their preferences for different attributes of the possible interventions, in order to assist the selection and detailed design of interventions for the main trial phase. Non-responding women in Aberdeen will be included to measure the effect of HPV vaccination in women's preferences. It is not envisaged that the results of the DCE would be used directly in the final economic evaluation, although it will be possible to compare stated preferences with revealed preferences manifested in uptake rates, and may also be possible to give estimates of values placed on attributes other than clinical effectiveness, such as convenience, control and confidentiality.

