6.2.3 Participants and recruitment

A sample of 2000 Manchester non-responders to cervical screening invitation separate to those invited into pilot interventions or into phase I will be recruited for the DCE. This figure is informed by work conducted by the ISPOR Conjoint Analysis Experimental Design Task Force in which simulation studies were used to explore the impact of alternative sample sizes on the precision of

parameter estimates. [Reed et al (2012) Constructing Experimental Designs for Discrete-Choice Experiments: Report of Value in Health. In press]. The screening agency, in conjunction with the researchers in Manchester, will identify non-responding women who are eligible to participate in the DCE study. Women will be sent a participant information sheet the paper-based version of the DCE and a FREEPOST envelope by the screening agency. As women will have the choice of whether to complete the paper-based version or to complete the DCE online (see section 6.24) the weblink for the online version will be provided in the patient information sheet. The paper-based DCE will be returned to York in the freepost envelope.

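### The discrete choice experiment has two conflicting sampling frames, and its 2000 is both the number invited and the number analysed

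*Protocol*

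**What the plan says.** Three parts of the protocol describe the sample for the discrete choice experiment (DCE).

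- **Section 6 (Economic Analysis and Organisational Impact Assessment):** "a sample of approximately 2000 non-responders to screening will be identified by the screening agency". It continues: "These women will be invited to state their preferences for different attributes of the possible interventions". On the frame it says: "Non-responding women in Aberdeen will be included to measure the effect of HPV vaccination".
- **Section 6.2.3:** "A sample of 2000 Manchester non-responders to cervical screening invitation separate to those invited into pilot interventions". The verb used for these women is recruited. The screening agency posts each woman an information sheet, the paper questionnaire and a prepaid envelope, and an online version is offered. Aberdeen is not mentioned. The figure of 2000 is attributed to task force simulation work on sample size and precision.
- **Section 6.2.5:** "A sample of 2000 non-responding women will be included in the DCE survey", and "A sample size of 2000 will provide a precision of 0.25-0.75 in the standard errors of the model coefficients". The same sentence says this sample allows a subgroup evaluation by setting, with the effect of HPV vaccination on preferences as its example.

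Two other places bear on the point. Section 3.3.1 looks ahead to "vaccinated women in England when they begin to receive their invitations 5 years from now". The timeline in 6.3 runs the DCE from mid January to mid March 2014 and lets its length depend on the response rate, but no expected rate is given anywhere.

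**The concern.** The three descriptions cannot all be true. A sample drawn only from Manchester has one setting, so it cannot support a comparison by setting. At the time of the survey it would also hold essentially no vaccinated women, so it cannot support a comparison by vaccination. Staff who follow 6.2.3, the section that governs recruitment, would mail Manchester alone. The vaccination question could not then be recovered from the data.

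Separately, one number does two jobs. In section 6 it counts women approached by post. In 6.2.5 it is the sample size to which a precision is attached. The two agree only if every woman replies, and these women are selected because they did not respond to a screening invitation. A precision figure for a sample that may not exist gives the reader no basis for judging what the DCE can show. Section 6 gives the DCE a role in choosing and shaping the interventions for the main phase.

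**Working it through.** **1. The stated precision.** The range 0.25 to 0.75 cannot be reproduced. The protocol gives no number of choice tasks, alternatives, attributes, levels, coding or prior coefficients. As a plausibility check only, take a binary conditional logit with coefficients near zero:

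SE = 1/√(n × T × 0.25 × E[Δx²])

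Here n is respondents, T is tasks per respondent, and E[Δx²] is the mean squared difference in an attribute between alternatives. The values are assumptions: T from 1 to 12 and E[Δx²] from 0.25 to 2.

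- Largest SE at n = 2000: 1/√(2000 × 1 × 0.25 × 0.25) = 0.089.
- Smallest SE at n = 2000: 1/√(2000 × 12 × 0.25 × 2) = 0.009.
- Choices needed in total for an SE of 0.25: 1/(0.25² × 0.25 × E[Δx²]), which is 256 at E[Δx²] = 0.25 and 32 at E[Δx²] = 2.

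A simple design would therefore do much better than the stated range, and a few hundred respondents could meet it. The figure is neither confirmed nor refuted.

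**2. Effect of non-return, taking the stated range at face value.** Suppose 0.25 to 0.75 applies to 2000 completed questionnaires and 2000 are mailed. The standard errors are then multiplied by √(2000/respondents) = 1/√(response rate). The response rates below are assumptions.

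| Assumed return | Respondents | Multiplier | SE range | Mailings for 2000 returns |
|---|---|---|---|---|
| 100% | 2000 | 1.00 | 0.25–0.75 | 2,000 |
| 50% | 1000 | 1.41 | 0.35–1.06 | 4,000 |
| 25% | 500 | 2.00 | 0.50–1.50 | 8,000 |
| 10% | 200 | 3.16 | 0.79–2.37 | 20,000 |

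**3. The sampling frame.**

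- 6.2.3: all 2000 from Manchester.
- Section 6: Aberdeen women included, with no number.
- 6.2.5: a setting or vaccination subgroup within the 2000.
- 3.3.1: vaccinated women in England start to be invited five years ahead. Counted from the protocol sign-off in January 2012 (8.2), that is about 2017. The DCE runs in early 2014.

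Under 6.2.3 the vaccinated share s is therefore essentially zero.

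**4. The vaccination contrast.** With share s in one group and equal information per woman, the SE of the difference in a coefficient is

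√(SE²/s + SE²/(1 − s)) = SE/√(s(1 − s)).

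- s = 0: not estimable at any sample size.
- s = 0.5: 1/√0.25 = 2, so 0.50–1.50 with all 2000 returned.
- s = 0.2: 1/√0.16 = 2.5, so 0.625–1.875 with all 2000 returned.

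So even with full return and an equal split, the contrast has twice the standard error quoted in 6.2.5. An equal split by site gives s = 0.5 for a comparison of settings. It does so for vaccination only if all the Aberdeen respondents and none of the Manchester respondents are vaccinated.

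**The case against.** The best defence is that the words leave room. Section 6.2.3 says the 2000 will be recruited and 6.2.5 says they will be included, so 2000 could mean completed questionnaires, and 6.3 shows that non-response was recognised. This stands in part: the protocol cannot be said to fix 2000 as the number mailed. It does not remove the defect. If 2000 is the number completed, section 6 is wrong and the number to be mailed is missing.

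It can also be said that section 6 and 6.2.5 agree in providing for Aberdeen, and that one word in 6.2.3 is out of line. That is fair. The contrast is lost only if 6.2.3 is followed, so the documents do not show that it will be lost.

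A reader might go further and infer that the stated precision will be missed, or that the coefficients will be too imprecise to rank the interventions. The documents support neither. The design inputs are absent, and the plausibility check shows that a simple design could meet these loose standard errors with far fewer than 2000 women. Whether interventions can be ranked depends on coefficient sizes and coding that are not given. Nor can a low return be read off the 25% first-invitation acceptance in section 1.1, because accepting a screening test is not the same as returning a questionnaire.

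The consequences are also limited. Section 3.4 takes interventions into phase 2 by a separate pilot test at a one-tailed 25% level, with agreement by the steering committee (8.2). Section 6 gives the DCE only an assisting role and does not expect to use its results directly in the final economic evaluation.

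**Conclusion.** The point holds as an internal inconsistency in an ancillary study. The firmer half is the frame. Sections 6, 6.2.3 and 6.2.5 conflict, and under 6.2.3 as written the vaccination contrast has essentially no information, whatever the sample size. This rests on the statement in 3.3.1 about when vaccinated women in England will be invited.

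The second half is that 2000 is undefined and the precision attached to it is unsupported. Its size depends on two assumptions: that 0.25 to 0.75 describes 2000 completed questionnaires, and what share is returned. Over an assumed 50% to 10% return, the standard errors are 1.41 to 3.16 times those stated. No primary trial analysis is affected. The correction is worth making because it is cheap and because a mailing to the wrong frame could not be repaired afterwards.

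**What to change.** Reconcile sections 6, 6.2.3 and 6.2.5 in one of two ways.

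- **Keep the vaccination question.** Amend 6.2.3 to divide the mailing between Manchester and Aberdeen with stated numbers. In 6.2.5, give the standard error for the vaccination contrast separately from the pooled one (twice the pooled value at an equal split).
- **Drop it.** Delete the subgroup claim in 6.2.5 and the Aberdeen sentence in section 6.

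In either case, say whether 2000 means invited or completed and use the same meaning throughout. Give an expected number of completed questionnaires with a range. Restate the standard errors for that number, together with the choice-task design they assume.

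The cost is mainly wording and a less favourable stated precision. Splitting the same mailing leaves a smaller Manchester sample, by an amount that depends on the split. If 2000 completed questionnaires are really wanted, the mailing must grow to 2000 divided by the assumed return, which is 8,000 at 25%.

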6.3 Timeline

February/early March: secure ethics approval (substantial amendment)
 Mid July to end September (10 weeks): Interviews and simultaneous data analysis
 Mid September 2013 to mid October 2013: Design and pilot DCE questionnaire
 Mid November 2013 to mid December 2013: secure ethics approval (substantial amendment)
 Mid January 2014 to mid March 2014 (depending on response rate): Run DCE
 March 2014 June 2014: DCE analysis

7. Direct access to source data/documents

The investigators will permit trial related monitoring, audits and regulatory inspections, providing direct access to source documents as and when required.

8. Ethics

8.1 Ethical arrangements

For phase 1 of the study we would seek to avoid the need for individual signed consent which would be impracticable for a study of this kind. Women would receive the pre-leaflet in addition to routine mailings from the Cervical Screening Programme, and would not be contacted directly by the researchers. No identifiable data will be passed from the screening agencies to the research team, and women will still receive the routine NHSCSP information which allows them to make an informed choice about attending for screening. Women receiving the pre-leaflet as part of the study will receive additional information which is designed to be more relevant to women attending for their first cervical screen. The outcome measure for this phase would be the rates of screening in practices randomised to their women receiving the information sheet compared to those who receive only the standard mailings, and therefore no patient details are required by the research team. Seeking individual consent to send the information sheet would require women to send their personal details to the research team when they are not necessarily being sought. Such a process of signing consent forms may also have the unintentional effect of deterring women from attending cervical screening. In order to monitor the number of women using the online booking service, clinic staff would be asked to provide the date of birth, GP and whether the woman attended the booked appointment for each booking made on the online system. The date of birth will be used to calculate how many months post invitation each woman was, whilst their GP practice details will allow the researchers to determine what proportion of women at each practice accepted the offer of online booking. Women will be informed that this information will be passed onto the research team at the time of booking the appointment. No identifiable data will be held on the trial database without explicit consent. Women will be offered the chance to make an online booking in the screening invitation letter they receive from the call/recall agency, and again the research team will not be given any personal identifiable data by the screening agency.

In phase 2, the only interventions whereby the woman would be required to donate time or undertake any action for no benefit is the discrete choice experiment, for which we would obtain informed consent. We would not seek personal details, such as a mobile phone number, without informed consent. Women in surgeries randomised to receive the offer of the nurse navigator or HPV self-sampling would be asked, via a reminder letter from the screening agency, to contact the research team to request the intervention. Women would then be able to be sent individual consent forms to give their consent for the research team to store their details for the purposes of checking the Exeter screening database to see whether they attend for screening as a result of the intervention. For the timed appointments, participating general practices would be asked to provide the same information as the clinics participating in online booking so the research team can identify how many women from each practice attended as a result of the intervention.

At no point will the research team be contacting the women directly, as the details of the women eligible for participation will be known only to the screening agencies. If women do not wish to accept the offer of the intervention they are free to do so and will not be sent any further trial related communications from the screening agency. As proportions of women attending for screening in each practice can be obtained from routine statistics, the research team do not require any personal details on the individuals unless they are required to enable the woman to participate in the intervention i.e. if they wish the nurse navigator to contact them, or they wish to be sent a HPV self-sampling test. As part of the pilot we would wish to send a small number of women (around 120) a HPV self-sampling test unsolicited to see what response rate is obtained. This would be facilitated by the screening agencies and women receiving the kit would be under no obligation to return it. The results of this exercise would be used to determine the most acceptable method of offering the intervention to women during phase 2 of the study.

8.2 Trial governance

The TSC met on 19:01:2012 and signed off the protocol; and will then convene at necessary time points during the trial to review progress, agree the taking forward of piloted interventions into phase 2, and advise the Trial Management Group when difficulties arise. The DMC would review the statistical plan, approve it and receive data at intervals specified by them. Independent members for the TSC include [name] (Professor of Gynaecological Oncology, UCL), [name] (Consultant Gynaecologist, Royal Free), [name] (Director of Jo's Cervical Cancer Trust) and [name] (Statistician, MRC).

9. Data handling and record keeping

9.1 Data management

The data management requirement for this project will largely involve processing and interpreting routine screening data. Screening agencies will be asked to supply anonymised data on an individual level for all women in the trial who have been screened each month in the control and intervention practices, along with the initial date of the women's invitations. A record will be maintained for each practice showing the number of women screened each month and the number of months post call each woman was when she attended for screening. This record will detail the date of the pre-notification list (PNL) for cervical screening, date of invitation, date of reminder letter, test due date, GP, date of the intervention, date of screening test, test result, venue sample obtained in (GP or family planning clinic), date woman changed GP and new GP details (where applicable).

The trial team will create a record for each woman who consents to having her data stored and cytology samples traced on the Exeter system as part of the phase 2 interventions. This record will detail the date of call, the woman's personal details and GP, the date of the intervention, the result of

the intervention i.e. a positive or negative HPV result or agreed to attend for screening after speaking to the nurse, and the date (and number of months post call) any subsequent cytology was taken. The trial team will collect data (as described in 6.1) in order to calculate the costs of delivering the interventions. Data will be stored securely on a University of Manchester or Central Manchester University Hospitals NHS Foundation Trust network drive and the PC will be password protected, in line with university data protection policy. Patient-identifiable information will be stored in a separate secure network location and linked to non-patient identifiable data by a unique identifier wherever possible. Access to patient-identifiable data will be strictly restricted to the trial team. A copy of the data will be burned onto a CD each month and stored in a fire proof safe within the department, and a second CD at another site.

10. Financial and Insurance Matters

The project is sponsored by the University of Manchester and funded by the NHS NIHR Health Technology Assessment Programme (Ref 09/164/01).

11. Publication Policy

